### 2.2 Hypotheses

**Aim 1: To determine the impact of COIN2DOSE and LOAN2DOSE as compared to control on the trajectory of glycemic control and treatment engagement among adolescents age 12-17 years who are at risk for a near-term rise in A1C.**

Hypothesis 1: Use of COIN2DOSE will result in a lower rise in A1C compared to the controls.

Hypothesis 2: Use of COIN2DOSE will improve engagement as measured by mealtime insulin BOLUS score compared to controls.

Hypothesis 3: Use of COIN2DOSE will yield sustained improvements in A1C trajectory for 12 weeks after the intervention.

Hypothesis 4: Use of COIN2DOSE will yield sustained improvements in BOLUS score for 12 weeks after the intervention.

Hypothesis 5: Use of LOAN2DOSE will result in a lower rise in A1C compared to the controls.

Hypothesis 6: Use of LOAN2DOSE will improve engagement as measured by mealtime insulin BOLUS score compared to controls.

Hypothesis 7: Use of LOAN2DOSE will yield sustained improvements in A1C trajectory for 12 weeks after the intervention.

Hypothesis 8: Use of LOAN2DOSE will yield sustained improvements in BOLUS score for 12 weeks after the intervention.

**Aim 2: To determine the feasibility of COIN2DOSE and LOAN2DOSE interventions in adolescents age 12-17 years who are at risk for a significant near-term rise in A1C.**

Hypothesis 9: The COIN2DOSE intervention will be feasible as determined by 1)  $\geq 75\%$  of participants in the intervention group will complete all study procedures for the duration of the intervention and post-intervention study periods, 2)  $\geq 75\%$  of parents will endorse the feasibility of providing an equivalent economic incentive plan, and 3) no decrease in quality of life at visit 2 compared to baseline (visit 1).

Hypothesis 10: The LOAN2DOSE intervention will be feasible as determined by 1)  $\geq 75\%$  of participants in the intervention group will complete all study procedures for the duration of the intervention and post-intervention study periods, 2)  $\geq 75\%$  of parents will endorse the feasibility of providing an equivalent economic loss aversion plan, and 3) no decrease in quality of life at visit 2 compared to baseline (visit 1).

**Aim 3: To determine user satisfaction with the COIN2DOSE and LOAN2DOSE intervention in adolescents age 12-17 years who are at risk for a significant near-term rise in A1C.**

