The objective of the present study is to obtain pilot feasibility data to 1) determine whether COIN2DOSE and/or LOAN2DOSE show a preliminary trend for improvement in the outcomes of interest, 2) perform power calculations that will inform the design of a definitive trial(s) and 3) establish feasibility of the interventions and study procedures to inform the design of a definitive trial(s).

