## 20.0 Data Management and Confidentiality

### 20.1 Statistical Analysis Plan

Database construction and management will involve acquisition of data from each source (see above), imported into Microsoft Excel or an equivalent database program. All analysis will be completed using Stata/SE 15.1 (StataCorp. 2017. Stata Statistical Software: Release 15. College Station, TX: StataCorp LLC), SPSS version 20, SAS version 9.4, other statistical programs as needed. Univariate analysis will be performed on all dependent and independent variables. Analysis includes determining whether the variables have non-normal distributions or outliers. Determinations then will be made as to whether the data transformations are needed. For example, if variance heteroscedasticity, exists, data will be analyzed using log-transformed or other transformations based upon Box-Cox approximations to normal distributions. Measures of other central dependency and dispersion will be evaluated. Primary analyses will be modified intention to treat analysis. All individuals who are randomized will be included in the analysis. A secondary per-protocol analysis may also be performed. Multivariable regression models will be examined to estimate the effects of study variables on the primary outcome – predicted trajectory of glycemic control base on A1C over 90 days – for this sample of T1D patients' data collected at three time points: baseline, 3 months, and 6 months. If the independent variables are highly correlated, we will explore General Linear Models (GLM) or other models. It is possible that Generalized Estimating

Equations (GEE) will be explored for their appropriateness in a larger study and/or for comparisons with the GLM results. Demographic and clinical variables will be entered into models following the independent variable: treatment group assignment. Since time effects may be important in the analyses due to treatments, censoring of data, time sequences, or other reasons, time of observation (i.e. visit 1[day 0], visit 2 [day 90], or visit 3 [day 180]) will also be explicitly accounted for in the regression models. All models will account for the clustering effect of participants having more than one clinic visit during the study timeframe. Additional variables will be collected as listed above. Statistical significance will be  $p<0.5$  (one-sided).

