### *20.2 Power analysis*

To evaluate the primary outcome: glycemic control (measures as predicted trajectory of A1C over 90 days), a multivariable regression model will be developed that accounts for seven independent variables: two primary – adherence and quality of life – and an additional five covariates: participant age, sex, insurance status, intervention/control group status, and time (52). Using an F-test and significant level (alpha) of 0.025, a sample of 20 T1D patients per treatment arm would achieve 74% power to detect an effect size of 0.35 (53). Findings from this pilot study will be used as estimates in planning future studies including recruitment of enough patients to achieve a power of greater than or equal to 80% to evaluate glycemic control (54).

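### Section 20.1 sets significance at one-sided p<0.5, very probably a slip for 0.05; even corrected, it matches the F-test alpha of 0.025 in section 20.2 in neither level nor sidedness

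*Protocol*

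**What the plan says.** Section 20.1 describes regression models for the primary outcome, the A1C trajectory over 90 days, and closes with "Statistical significance will be $p<0.5$ (one-sided". No other passage gives a significance rule, and no entry in the revision history corrects this one.

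Section 20.2 takes the same primary outcome and states: "Using an F-test and significant level (alpha) of 0.025, a sample of 20 T1D patients per treatment arm would achieve 74% power", for an effect size of 0.35. It gives no sidedness. The model has seven independent variables, described as "two primary – adherence and quality of life – and an additional five covariates"; intervention/control status is one of the five covariates.

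The efficacy hypotheses in section 2.2 are directional and separate for each active arm: "Hypothesis 1: Use of COIN2DOSE will result in a lower rise in A1C compared to the controls" and "Hypothesis 5: Use of LOAN2DOSE will result in a lower rise in A1C compared to the controls". Section 4.0 defines the primary outcome as the change in A1C from baseline to the 90-day visit.

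**The concern.** A significance level of one half is not a usable criterion, since a directional test at that level rejects whenever the estimate has the hoped-for sign. A lost zero is the obvious explanation, and a reader may mentally substitute 0.05 and move on. That does not settle the matter, because section 20.2 uses a different number for the same outcome, attached to a test that is not one-sided.

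At stake is the label put on the primary A1C comparisons and on the other tested outcomes. If the level is unresolved when the data arrive, a one-sided p-value between 0.0125 and 0.05 for an arm contrast could be called significant under section 20.1 with the digit corrected, and not significant under section 20.2 read as a test on one degree of freedom. Section 2.1 says that the results, if initially efficacious, will support a grant application, so the label will be read by others.

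**Working it through.** **Inputs.** Level p<0.5, one-sided (section 20.1). F-test, alpha 0.025, 20 per arm, effect size 0.35, power 74%, seven model variables of which two are called primary (section 20.2). Three arms, 1:1:1 (section 11.0). Not given, and therefore assumed where used: the metric of the effect size, the tested terms and the degrees of freedom.

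**1. The plan's own power figure.** Take two tested terms (u = 2), five controlled, N = 40 (two arms of 20), v = 40 − 2 − 5 − 1 = 32, effect size read as f² = 0.35, and noncentrality f²·v = 0.35 × 32 = 11.2. Noncentral-F power is:

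| F-test alpha | Power |
|---|---|
| 0.025 | 73.0% |
| 0.05 | 82.3% |
| 0.5 | 99.2% |

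So 74% is approximately reproduced at 0.025. The reproduction is not unique. Other noncentrality conventions give 77.5% (f²(u+v+1)) and 83.5% (f²N) at 0.025. N = 60 with one tested term, no controlled terms and the effect size read as f = 0.35 (f² = 0.1225, v = 58, noncentrality f²·v) gives 74.6% at alpha 0.05. A one-way three-arm comparison at 20 per arm with f = 0.35 gives 54.0% at 0.025. The 74% is therefore compatible with 0.025 but does not identify the test behind it. Nothing below depends on this step except where stated.

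**2. The literal rule.** The critical value at one-sided 0.5 is z = Φ⁻¹(0.5) = 0, so any favourable difference qualifies and the false-positive rate per ineffective arm is 50%. Two active arms sharing a control of equal size have test statistics correlated at ρ = 0.5. The chance that neither is positive is 1/4 + arcsin(0.5)/(2π) = 0.2500 + 0.0833 = 0.3333, so the chance of at least one false positive is 1 − 0.3333 = 66.7% (large-sample).

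**3. The digit corrected.** At one-sided 0.05, z = 1.645, and the same calculation, 1 − Φ₂(z, z; 0.5), gives 8.8% for at least one of two ineffective arms, with no adjustment.

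**4. Level and sidedness.** For a contrast on one degree of freedom F = t², so an F-test at alpha a rejects when |t| exceeds its upper a/2 point. Each direction then has level a/2.

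| F-test alpha (1 df) | One-sided level |
|---|---|
| 0.025 | 0.0125 |
| 0.05 | 0.025 |
| 0.10 | 0.05 |

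Thus F at 0.025 differs from one-sided 0.05 by a factor of four, not two. Halving one-sided 0.05 over the two active arms gives one-sided 0.025, which is F at 0.05, so that split does not arrive at section 20.2's figure. With two or more numerator degrees of freedom the F-test has no direction, and a one-sided level cannot be attached to it.

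**5. What the mismatch would do to power, if the 74% belonged to a contrast on one degree of freedom.** Solve for the noncentrality that gives 74% at F 0.025, with v scanned from 12 to 70, then evaluate the directional t-test. Power is 82.6% to 84.2% at one-sided 0.025 and 89.7% to 91.8% at one-sided 0.05. This is conditional, because section 20.2 does not say that its F-test is an arm contrast.

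**The case against.** The strongest reply is that 0.5 is a transparent typing error, possibly a zero lost in reading the PDF, and nobody would apply it. The trial is a pilot meant to "determine whether COIN2DOSE and/or LOAN2DOSE show a preliminary trend for improvement in the outcomes of interest", no p-value gates the definitive trial, and an unadjusted one-sided 0.05 is defensible in that setting. Power computed at a stricter level than the one used for testing errs on the cautious side. Much of this stands: the 50% and 66.7% rates describe a rule that is unlikely to be carried out, and the practical effect is limited to reporting. It does not remove the error, since the stated rule is unusable and the substitute value is still at odds with section 20.2.

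Three stronger readings are tempting and are not supported:

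- A reader might infer that 0.025 is 0.05 split over the two active arms, so that the sections agree once the zero is restored. Neither section says so, and for a directional contrast the conversion fails (step 4). The split might equally be over adherence and quality of life, the variables section 20.2 calls primary.
- A reader might infer that the 74% is the power for each active arm against control. Section 20.2 lists group status among the covariates and does not say which terms its F-test covers.
- A reader might infer that the choice of level carries this trial past an 80% power requirement. Section 20.2 attaches that figure to future studies: "recruitment of enough patients to achieve a power of greater than or equal to 80".

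**Conclusion.** The point holds. The protocol's sole significance criterion is wrong as written, and replacing 0.5 with 0.05 leaves two unlinked levels for the same primary outcome that also differ in sidedness. The literal size is 50% false positives per ineffective arm and 66.7% for either of two; the realistic remainder is one-sided 0.05 against the one-sided 0.0125 implied by an F-test on one degree of freedom at 0.025, or no one-sided equivalent at all if the F-test has several.

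That the slip was for 0.05 is an inference; no passage states 0.05. The two-arm rates are large-sample and treat the two active-arm comparisons as a pair, which the protocol does not formally do. The contradiction itself rests on the text alone. It affects which results are called significant; the feasibility and satisfaction outcomes have their own criteria and are untouched. It should be corrected because a decision threshold is invalid and the repair is small.

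**What to change.** In section 20.1, replace p<0.5 with the intended level and tie it to named comparisons. Possible wording, if no adjustment is meant: *COIN2DOSE and LOAN2DOSE are each compared with control on 90-day A1C change at one-sided p<0.05, without adjustment for the two comparisons.* If an adjustment is meant, give the adjusted one-sided level and name the tests over which it is divided.

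In section 20.2, state which terms the F-test covers. If it is an arm contrast on one degree of freedom, make its alpha agree with section 20.1: F-test alpha 0.10 for one-sided 0.05, or 0.05 for one-sided 0.025. If 0.025 belongs to a different test, such as that of adherence and quality of life, say so and give the level for the arm comparisons separately. Restate the 74% power for the level and test finally chosen.

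The cost is one sentence in each section and one recalculated power figure, with no change to procedures. A stricter level than the one now intended would lower power.

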### *20.2 Power analysis*

To evaluate the primary outcome: glycemic control (measures as predicted trajectory of A1C over 90 days), a multivariable regression model will be developed that accounts for seven independent variables: two primary – adherence and quality of life – and an additional five covariates: participant age, sex, insurance status, intervention/control group status, and time (52). Using an F-test and significant level (alpha) of 0.025, a sample of 20 T1D patients per treatment arm would achieve 74% power to detect an effect size of 0.35 (53). Findings from this pilot study will be used as estimates in planning future studies including recruitment of enough patients to achieve a power of greater than or equal to 80% to evaluate glycemic control (54).

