## 1.0 Study Summary

Study Title	HCT Cash-Only IN centive to promote mealtime insulin DOSE Engagement (HCT COIN2DOSE): a pilot trial
Study Design	Pilot randomized controlled trial
Primary Objective	To determine the impact of HCTCOIN2DOSE and LOAN2DOSE compared to control on the trajectory of glycemic control and treatment engagement among adolescences age 12-17 years who are at risk for a near-term rise in A1C.
Secondary Objective(s)	To determine both the feasibility and usability of HCTCOIN2DOSE and LOAN2DOSE intervention compared to control in adolescents age 12-17 years who are at risk for a significant near-term rise in A1C.
Research Intervention(s)/ Investigational Agent(s)	HCT COIN2DOSE: Utilization of immediate financial incentives to promote mealtime insulin dose delivery, with weekly bonuses for sustained meal dosing behavior LOAN2DOSE: Utilization of loss aversion approach to promote mealtime insulin dose delivery. Participants will start with a virtual bank balance and will have money deducted from the balance when mealtime insulin doses are missed. Additional amounts will be deducted when sustained meal dosing goals are not met.
IND/IDE #	NA
Study Population	Individuals identified by artificial intelligence who are predicted to experience a rise in A1C of greater than or equal to 0.3% in the next 70-110 days using a validated predictive algorithm created via advanced machine learning (random forest) and natural language processing. Individuals must have had the diagnosis of T1D for 6 months and be 12-17.99 years old. Parents of children who meet inclusion criteria may choose to participate in the focus group
Sample Size	A minimum of 36 and a maximum of 72 youth randomized in a 1:1:1 ratio to either the treatment or usual care (control).  Participants and their parents may choose to participate in the focus group. Parents may enroll in the focus group if their child is enrolled in the study. Our aim will be to enroll 5 to 30 parents.
Study Duration for Individual Participants	26 weeks (11-13 weeks intervention and 11-13 weeks observation Participants and/or their parents may choose to participate in a focus group at the end of the study (week 26).

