## 2.0 Objectives

### 2.1 Primary Objectives

The long-term goal is to develop effective ways to improve glycemic control in youth with T1D. To that end, we propose to specifically evaluate the effectiveness, feasibility, and usability of two new interventions in diabetes care: an economic incentive (COIN2DOSE) and an approach that uses an economic loss aversion (LOAN2DOSE) to promote patient engagement with mealtime insulin dosing behavior. If initially efficacious, our results will serve as the basis for an R01 submission(s) to conduct a fully powered efficacy trial of COIN2DOSE and LOAN2DOSE. This study is significant as omission of mealtime boluses is one of the common reasons for suboptimal diabetes control in youth. This project is highly innovative because it will: 1) target youth who are predicted by artificial intelligence to experience a worsening in glycemic control, 2) use an economic incentive intervention to improve mealtime insulin dosing behavior and 3) use an economic loss aversion to improve mealtime insulin dosing behavior.

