## 4.0 Study Endpoints

### Outcome Measures

Primary outcome:

- 1) Change in A1C ( $\Delta A1C_{90\text{-day}}$ ) from baseline visit (visit 1) to 90-day visit (visit 2).

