## 11.0 Inclusion and Exclusion Criteria

Individuals who have been predicted via an artificial intelligence-intelligence based model to experience a rise in A1C in the near future (90 days) will be approached for recruitment. 36 participants will be recruited from the Children's Mercy Diabetes Center (any clinic or hospital location). Based on preliminary data review of our clinic population, there were at least 81 individuals who met inclusion criteria who were seen in clinic in the month of May 2019 alone. Patients will be randomized to, COIN2DOSE, LOAN2DOSE, or control group using a 1:1:1 randomization scheme.

Inclusion Criteria:

- 1) Aged 12-17.99 years
- 2) The youth must have been diagnosed with T1D for at least 6 months
- 3) The youth must have attended at least 2 routine T1D standard of care visits in the past 12 months

- 4) The youth must be using an insulin delivery device capable of recording, storing, and downloading insulin bolus behaviors (insulin pump or smart Bluetooth insulin pen that can be uploaded to standard clinic upload software).
- 5) The youth must have a current A1C >7.2% and/or be predicted to have a rise in A1C in of 0.3% or higher the next 90 days.
- 6) Not pregnant or planning to become pregnant by self-report.

Exclusion Criteria:

- 1) Participants with any type of diabetes mellitus other than T1D
- 2) Participant has any disease-causing anemia or affecting red blood cell physiology (which would impact A1C)
- 3) Participant has a physical disability, which in the opinion of the investigator would interfere with individual's ability to feed themselves or use one's hands to facilitate eating
- 4) Participants with no internet access or ability to upload device(s) to data aggregation software that is accessible to study team.

For Focus Groups:

Any parent or legal guardian whose child is participating in the study is invited to participate in a focus group discussion.

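### Sections 20.1 and 20.2 name the primary outcome as an undefined predicted trajectory of A1C, not the visit 1 to visit 2 change that Section 4.0 declares

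*Protocol*

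**What the plan says.** The protocol describes the primary outcome in three places.

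- **Section 4.0, Primary outcome:** the change in A1C "from baseline visit (visit 1) to 90-day visit (visit 2". This is a difference between two measured values.
- **Section 20.1, Statistical Analysis Plan:** the primary outcome is "predicted trajectory of glycemic control base on A1C over 90 days", analysed with "data collected at three time points: baseline, 3 months, and 6 months".
- **Section 20.2, Power analysis:** the primary outcome is "glycemic control (measures as predicted trajectory of A1C over 90 days".

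Section 20.1 adds time of observation as a model term and states: "All models will account for the clustering effect of participants having more than one clinic visit during the study timeframe". Section 4.0 lists the change from visit 1 to the 180-day visit as a secondary outcome.

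Outside Section 20, the word predicted, when applied to A1C or glycemic control, describes how patients are selected. The Study Summary speaks of youth "predicted to experience a rise in A1C of greater than or equal to 0.3% in the next 70-110 days", Section 2.1 of a plan to "target youth who are predicted by artificial intelligence to experience a worsening in glycemic control", and Section 11.0 of "Individuals who have been predicted via an artificial intelligence-intelligence based model to experience a rise in A1C". Section 5.0 describes the same model, with a 90-day horizon.

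**The concern.** A primary outcome should be the same variable where it is declared, where it is analysed and where it is powered. Here the declaration gives one variable, and the two statistical sections give another name that is not explained. The phrase occurs in both statistical sections, so it is not a single slip, and neither section mentions the visit 1 to visit 2 change.

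Three things are at stake. First, the power statement is attached to the undefined outcome, so it cannot be read as power for the declared one. Second, Section 6.0 describes an unblinded trial. With two descriptions of the primary outcome in force, and data to 6 months feeding the model, the choice of what counts as primary can be made after results are seen. Third, Sections 3.2 and 20.2 say that this pilot will supply estimates for a definitive trial. Effect and variance estimates depend on which outcome they belong to.

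**Working it through.** **Step 1. Is the term defined anywhere?** No. Trajectory appears in the primary objective (Section 1.0) and in Hypotheses 3 and 7 (Section 2.2) as something that the interventions should improve. Predicted appears in Sections 1.0, 2.1, 5.0 and 11.0 for the forecast before enrolment. The two words are joined only in Section 20, without a definition.

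**Step 2. Which readings equal the Section 4.0 outcome?** Write A1, A2 and A3 for measured A1C at visits 1, 2 and 3, taken at days 0, 90 and 180 as in Section 20.1. Table 1 schedules A1C only at these visits.

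- *Slope through visits 1 and 2 only:* (A2 − A1)/90 per day, or A2 − A1 per 90 days. This is the Section 4.0 change, apart from visit-window scaling.
- *One straight line through all three visits:* the centred times are −90, 0 and +90. The least-squares slope is (−90·A1 + 0·A2 + 90·A3)/(90² + 90²) = (A3 − A1)/180 per day, or (A3 − A1)/2 per 90 days. Visit 2 has weight zero. The result is half the secondary 180-day change.
- *A treatment-group term averaged over all three visits, with time as a factor and no group-by-time term:* let the true between-arm differences be 0 at visit 1 (randomised), d2 at visit 2 and d3 at visit 3. With complete data the group coefficient has expectation (0 + d2 + d3)/3. It equals d2/3 if the effect has gone by visit 3, and 2·d2/3 if it is fully sustained.

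The last two are illustrations. They assume complete data and, for the straight line, equal spacing. Section 20.1 does not say that either will be used. They show that its list of ingredients (treatment group, time, three visits, clustering) does not by itself lead back to A2 − A1.

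**Step 3. Does the power figure settle which outcome was meant?** Section 20.2 gives an F-test, alpha 0.025, 20 per arm, effect size 0.35, seven independent variables and 74% power. It does not give the tested degrees of freedom (u), the total N used or the scale of the effect size. With k = 7 predictors, v = N − 8 and noncentrality λ = N·f², power is the probability that a noncentral F(u, v, λ) exceeds the 97.5th percentile of F(u, v).

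| Reading of 0.35 | Total N | Tested df | Power |
|---|---|---|---|
| f² | 40 | 2 | 83.5% |
| f² | 40 | 7 | 55.9% |
| f² | 60 | 2 | 96.8% |
| f² | 60 | 7 | 83.7% |
| f, one-way ANOVA with three groups | 60 | 2 | 54.0% |

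Readings that come within two points of 74% need inputs that Section 20.2 does not state. Examples are N = 20 in total with one tested df and R² = 0.35 (75.5%), or alpha 0.0125 with N = 60, seven tested df and f² = 0.35 (75.8%). The 74% can be neither confirmed nor refuted, so it does not show which outcome was in mind. Section 20.2 also lists group status among five covariates and does not say that the group term is the one tested.

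**The case against.** The best defence is that this is loose drafting. Section 4.0 is unambiguous. Section 20.1 works with measured data at three visits, and the hypotheses treat the A1C trajectory as modifiable. In a regression section, predicted may simply mean model-fitted. A1C is measured at only two points within the first 90 days, so a trajectory over 90 days would then be the Section 4.0 change under another name. Model details such as a visit 2 contrast may also stand in a separate analysis plan that is not at hand.

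Much of this stands. It makes the benign reading plausible, and the absence of a contrast would not be a finding alone. It does not remove the contradiction: the protocol's own statistical section gives the outcome a different name, and the inclusion of 6-month data prevents a reader from simply equating the two.

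Two stronger readings are tempting, and the text does not support them. A reader might infer that Section 20 analyses the algorithm's forecast, which is fixed before allocation and could show no treatment effect. Repeated visits, a time term and within-participant clustering do not fit a single fixed forecast. A reader might also infer an outcome of observed minus forecast A1C, with forecast error added to the noise. No section subtracts one from the other.

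**Conclusion.** The point holds as an inconsistency in naming and defining the primary outcome. Section 4.0 declares the measured change from visit 1 to visit 2. Sections 20.1 and 20.2 name an undefined predicted trajectory, and Section 20.1 gives it a 90-day label but 6-month data. The declared endpoint is not the stated target of the analysis or of the power calculation.

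No numerical loss can be attached, because the intended quantity is not stated. It ranges from none, if only visits 1 and 2 are meant, to estimating the secondary outcome instead, if one line is fitted through all three visits. Nor does this show that the 74% is wrong; it is only untied to the declared outcome. The correction should be made before analysis.

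**What to change.** - In Sections 20.1 and 20.2, replace the predicted-trajectory wording with the Section 4.0 outcome, the observed change in A1C from visit 1 to visit 2.
- In Section 20.1, state that the primary comparison is the between-arm difference in that change, and that visit 3 data serve the secondary 180-day outcome.
- In Section 20.2, recheck the power statement against that comparison, giving the tested term, total N and effect-size scale. Restate the figure if it does not apply. Changing the outcome label alone would not make the 74% valid for the declared endpoint.

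The cost is wording in two sections and one repeated power calculation. No visit, measurement or participant is added.

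### Sections 20.1 and 20.2 disagree on which term of the primary A1C model answers the trial's question, and 20.2's version can adjust away the treatment effect

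*Protocol*

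**What the plan says.** Section 20.1 describes multivariable regression for the 90-day A1C trajectory and states: "Demographic and clinical variables will be entered into models following the independent variable: treatment group assignment". It names neither adherence nor quality of life. It also builds visit time (days 0, 90 and 180) into the models and allows for repeated visits per participant.

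Section 20.2 describes a regression for the same primary outcome with seven independent variables: "two primary – adherence and quality of life – and an additional five covariates: participant age, sex, insurance status, intervention/control group status, and time". With an F-test at alpha 0.025, 20 patients per arm "would achieve 74% power to detect an effect size of 0.35". It does not say which term is tested, on what scale 0.35 is measured, or whether adherence and quality of life are baseline or follow-up values.

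Section 2.2 sets the question. Hypothesis 1 reads "Use of COIN2DOSE will result in a lower rise in A1C compared to the controls" and Hypothesis 5 reads "Use of LOAN2DOSE will result in a lower rise in A1C compared to the controls". Section 4.0 defines the primary outcome as the A1C change between visits 1 and 2.

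**The concern.** Both sections describe the model for the primary outcome, and they give treatment group different roles. Only the 20.1 version addresses Aim 1.

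The choice of leading variables matters because adherence is not an ordinary covariate here:

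- It is the behaviour for which COIN2DOSE pays and LOAN2DOSE deducts (section 5.0).
- The hypotheses predict that treatment will change it: "Use of COIN2DOSE will improve engagement as measured by mealtime insulin BOLUS score compared to controls" (Hypothesis 2; Hypothesis 6 says the same for LOAN2DOSE).
- Change in BOLUS score is secondary outcome 6 (section 4.0).
- The rationale in section 3.2 names it as the route to better glycaemic control.

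Quality of life at visit 2 is likewise an outcome, as a feasibility criterion in Hypotheses 9 and 10.

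A model that conditions on post-randomisation adherence no longer estimates the total effect of assignment. It asks what the incentive does to A1C apart from changing mealtime dosing. Section 3.2 says the pilot should show a preliminary trend and supply inputs for powering a definitive trial. Both uses need the total effect of each arm against control.

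**Working it through.** **1. The two sections side by side**

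| | 20.1 | 20.2 |
|---|---|---|
| Outcome | A1C trajectory over 90 days | A1C trajectory over 90 days |
| Leading variable(s) | Treatment group | Adherence, quality of life |
| Treatment group | The independent variable | One of five covariates |
| Adherence, quality of life | Not named | The two primary variables |

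The list under Covariate Measures in section 4.0 (age, sex, race, diabetes duration, depression) contains neither adherence nor quality of life.

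**2. Which values could enter**

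The schedule in section 10.0 has device downloads and the quality-of-life questionnaire at visits 1, 2 and 3, with further downloads in between. Both sections put time in the model. Follow-up values are therefore available and could be entered under 20.2 as written.

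**3. Consequence if post-randomisation adherence enters**

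Let e be the total effect and m the share acting through adherence. In a linear model with no interaction and no confounding of adherence and A1C, the group coefficient given adherence is e − m·e = (1 − m)·e. The Protocol does not give m, so only the range can be shown:

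| m | Share of effect retained |
|---|---|
| 0 | 100% |
| 0.5 | 50% |
| 1 | 0% |

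A simulation on assumed values (20 per group, 2,000 runs, true total effect −0.5) agrees. With m = 0.25, 0.5, 0.75 and 1, the adjusted coefficient averaged −0.38, −0.25, −0.15 and 0.00. Without adherence in the model it stayed between −0.50 and −0.52. Baseline adherence would produce no such loss.

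**4. Does the stated 74% belong to an arm contrast?**

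Inputs from 20.2: 20 per arm × 3 arms = 60 participants, p = 7 variables, alpha 0.025, effect size 0.35. Assuming one record per participant, denominator df = 60 − 7 − 1 = 52. Power comes from the noncentral F distribution with noncentrality N·f².

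- If 0.35 is f²: 60 × 0.35 = 21.0.
- If 0.35 is f: f² = 0.35² = 0.1225, and 60 × 0.1225 = 7.35.

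| Term tested | df | Critical F | Power, f² = 0.35 | Power, f = 0.35 |
|---|---|---|---|---|
| Group as one term, as 20.2 counts it | 1 | 5.33 | 98.7% | 65.7% |
| Adherence + quality of life | 2 | 3.96 | 96.8% | 53.7% |
| All seven variables | 7 | 2.54 | 83.7% | 29.5% |

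None of the six is 74%.

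Three arms need two group indicators, so the group test has 2 df, the model has 8 terms, and denominator df = 60 − 8 − 1 = 51. Power is then 96.7% (f² = 0.35) or 53.6% (f = 0.35). With the alternative noncentrality f²·(u + v + 1), where u and v are the numerator and denominator df, it is 94.8% or 48.5%.

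A close match to 74% needs inputs that 20.2 does not state. N = 40, two terms tested in a model of nine, f² = 0.35 and noncentrality 0.35 × (2 + 30 + 1) = 11.55 give 74.2%. That would fit a two-arm total and a test of two added variables, but this is inference only.

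**The case against.** The strongest reply is that the harm rests on silence. Nothing in 20.2 says follow-up values enter, which visit's value is used is often settled in a separate analysis plan, and with baseline values the group coefficient is sound whatever label it carries. This stands as a limit: the bias is conditional. It does not remove the conflict, because 20.2 says the model it describes will be developed to evaluate the primary outcome, and 20.1 describes that model differently.

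Second, 20.1 admits unspecified clinical variables after group, so adherence and quality of life could be among them. That is fair. The firm contradiction is over which term is primary, not over which variables may appear.

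Third, the power figures assume one record per participant, yet with a single visit 1 to visit 2 change the time term would be constant. The one-df group row also does not fit three arms. Both points are correct. The figures test 20.2's own count of variables on a simplifying assumption, and the 2-df calculation is the one relevant to three arms. They show only that 74% cannot be traced to an arm contrast from the stated inputs.

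Fourth, adherence is not randomised, so conditioning on it after baseline could bias the coefficient in either direction. This also stands: 1 − m holds only without confounding.

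**Conclusion.** The concern holds. Sections 20.1 and 20.2 contradict each other on the primary term of the primary model, and Aim 1 with Hypotheses 1 and 5 requires the 20.1 version. This part rests on the text alone.

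The bias is conditional on post-randomisation adherence entering the model. Its size cannot be derived from the Protocol: anywhere from none to all of the effect could be lost under the linear, unconfounded case, and confounding could push the estimate either way.

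The 74% is not shown to be power for an arm-versus-control contrast. No replacement figure can be given, because the scale of 0.35 is not stated and the two readings differ by more than 40 percentage points for the three-arm test (96.7% against 53.6%). This should be fixed before analysis.

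**What to change.** Reconcile the two sections so that they describe one primary model:

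- Make COIN2DOSE versus control and LOAN2DOSE versus control the tested terms, on the A1C change from visit 1 to visit 2.
- Allow adherence and quality of life into that model only as baseline values. Put their post-randomisation values in a separate analysis labelled exploratory.
- In the power sentence, name the arm contrast as the tested term, state whether 0.35 is f, f² or another measure, and restate the power for that contrast.

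The cost is revised wording in 20.1 and 20.2 and one recalculated power figure. All the data needed are already scheduled.
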